9. Subjects involved in litigation regarding injury or worker's compensation benefits.	9. History, self-report
10. Subjects with a diagnosis of vasculitis, peripheral vascular disease, peripheral neuropathy, small-fiber neuropathy, or fibromyalgia.	10. Medical history, self-report.

Subject Screening:

Subjects will be referred to the study from the Addiction Institute Opioid Treatment Program. Subjects will also be recruited by word of mouth, fliers, newspaper advertisements, and postings on relevant websites. Contact information will be provided so that potential subjects may speak with a research coordinator/research assistant to learn more about the opportunity to participate in the study. Potential participants will take part in a brief phone interview to establish pre-eligibility. Pre-eligible participants will be given an appointment for a screening visit.

They will then undergo additional screening for the study, including a SCID, review of metal implants, pregnancy test (if indicated), medical history, physical exam, vital signs (HR, BP, temp), TASS, and consent for study procedures. For all females of child-bearing potential, a pregnancy test will be repeated prior to beginning rTMS sessions. Daily medication use will be assessed for the 4 weeks prior to study entry using the time-line follow back procedure.

Following screening, the subjects will undergo the following procedures:

- 1) Pregnancy tests will be performed weekly during rTMS and before each MRI. Before the rTMS begins, we will perform an initial determination of motor threshold. Subjects with a motor threshold of 85% (of maximal stimulator output) at the initial determination of motor threshold will be removed from the study. The rationale for this is that, in our experience, high motor thresholds of this level result in discomfort and anxiety when the actual rTMS sessions are delivered.
- 2) Volumetric MRI and MRS scans.
- 3) Baseline neuropsychological testing, including pain scales.
- 4) Five weeks of rTMS, Monday – Friday, on an outpatient basis. The pain scales will be performed during the weeks of rTMS, up to daily.
- 5) Repeat volumetric MRI and MRS scans after the rTMS.
- 6) Repeat neuropsychological tests after the rTMS.

Neuropsychological scales and tests: Subjects will be asked to complete the following tests and scales before and after the sessions of rTMS (at baseline and after the completion of the rTMS).

Scales (expected to take 60 minutes total):

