The effect of rTMS on chronic pain will be performed with a repeated measure ANOVA. Post-hoc contrasts between the groups will be assessed with t tests with correction for multiple comparisons. Groups will be prospectively matched for variables suspected to influence the outcome measures (age, gender, ethnicity). The effect of these variables on each dependent variable will be assessed by ANOVA. In case of significant or near significant effect ($p < 0.10$), these variables will be included in the model (ANCOVA). For all analyses described above, a two tailed probability value of $p < 0.05$ will be selected as significance threshold and correction for multiple comparisons will be applied. In case of nonnormality or inhomogeneity of variance, we will first evaluate data transformation techniques (log or square root) to address these issues. If this cannot be achieved, we will use nonparametric tests, or bootstrap analysis.

Criteria for Early Discontinuation

Subjects will be assessed at least weekly by a study psychiatrist. Subjects will be removed from the study if they experience a worsening of depressive symptoms or an HRSD > 17 . Any answer of “yes” on the Columbia Suicide Severity Rating Scale or a score of > 10 on the Young Mania Scale will require a psychiatric evaluation to determine if continuation in the study is appropriate.

A Clinical Global Impression-improvement score and CGI opioid improvement score will be obtained weekly by a study physician. Subjects will be assessed, by a study physician, for continuation in the study if they score 6 or 7.

Risks associated with the study:

1. MRI scans.

The scan may be dangerous if combined with magnetic objects in the body. While there have been no reports of any harmful long-term effects caused by the MRI scanner, including magnets of high strength, the long-term effects of being placed in a magnet of the strength used in this study is unknown. Subjects with metallic objects in their body which would exclude them from receiving an MRI for clinical purposes are excluded from the

study. Also, although there are no known risks associated with pregnancy, subjects will not be included if pregnant.

2. Reduction in opioid use.

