c. Headache: A mild headache, which responding readily to non-opioid analgesics is the most common side-effect reported in depression treatment trials. All volunteers will be treated with NSAIDs as needed for headache.

d. Hearing Impairment: Rapid excitation of the stimulation coil produces clicks that have resulted in transient increase in the auditory threshold, which does not occur if earplugs are used. A previous study assessed the auditory threshold before and after 30 sessions of rTMS (over 6 weeks) in subjects wore earplugs during stimulation and no significant mean changes were detected. All participants will wear earplugs during the delivery of stimulation.

e. Additional risks include scalp pain, dental pain, and rTMS-induced manic effect. Subjects will be evaluated for each of these and treated with over the counter pain medications if required for the scalp and dental pain. Subjects will also be evaluated for an rTMS-induced manic effect. If mania occurs, they will be removed from the protocol and monitored until these symptoms resolve.

f. Additional risks include scalp pain and rTMS-induced manic effect. Subjects will be evaluated for each of these and treated with over the counter pain medications if required for the scalp and dental pain. Subjects will also be evaluated for an rTMS-induced manic effect. If mania occurs, they will be removed from the protocol and monitored until these symptoms resolve. Convulsive 14 syncope has also been reported, and we will take the following measures to prevent this: participants will be asked to immediately report any symptoms of syncope (e.g. feeling dizzy, light headed, visual changes) and will be placed in the supine position with elevated legs if syncopal symptoms appear.

5. Risks associated with the psychological test battery include potential nervousness and frustration with the tasks. A member of the research team will carefully explain the tests before hand and will be available for questions during the tasks should they arise.

Adverse Event Reporting

Timely, accurate, and complete reporting and analysis of safety information from clinical studies are crucial for the protection of subjects and investigators, and are mandated by regulatory agencies worldwide.

1. Adverse Event Definitions and Classifications

• Adverse Event

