The PI assumes responsibility for appropriate reporting of adverse events to the regulatory authorities. The investigator will report these events to the appropriate Institutional Review Board, which approved the protocol unless otherwise required and documented by the IRB.

5. Serious Adverse Event Reporting Procedures

All serious adverse events occurring during clinical studies must be reported to the PI by investigational staff within 24 hours of their knowledge of event. Information regarding serious adverse events will be recorded on the Serious Adverse Form, which must be signed by a member of the investigational staff.

All serious adverse events that have not resolved by the end of the study, or that have not been resolved upon discontinuation of the subject's participation in the study must be followed until any of the following occurs:

- The event resolves
- The event stabilizes
- The event returns to baseline, if a baseline value is available
- The event can be attributed to agents other than the study treatment or to factors unrelated to study conduct

The cause of death of subject in a clinical study, whether or not the event is expected or associated with the investigational agent, is considered a serious adverse event. Any event requiring hospitalization (or prolongation of hospitalization) that occurs during the course of a subject's participation in a clinical study must be reported as a serious adverse event, except hospitalization for:

- Pre-planned hospitalizations, i.e. before enrollment into the study and which are not related to the disease itself
- Social reasons in absence of an adverse event
- Surgery or procedure planned before entry into the study (must be documented in the CRF)

6. Pregnancies

Pregnancies occurring during the study must be reported by the investigational staff within 1 working day of their knowledge of the event. Any subject who becomes pregnant during participation in a clinical study for which pregnancy is a standard exclusion criterion must be promptly withdrawn from the study.

Confidentiality

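### No pain or opioid-use assessment is scheduled after early removal, and the primary responder proportion has no stated denominator or missing-response rule

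*Combined protocol and SAP*

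**What the plan says.** **Routes out.** The Criteria for Early Discontinuation say that "Subjects will be removed from the study if they experience a worsening of depressive symptoms", with a Hamilton depression score above 17 as an alternative trigger. For mania, the rTMS risk section says: "If mania occurs, they will be removed from the protocol and monitored until these symptoms resolve". Under Pregnancies, a participant who becomes pregnant "must be promptly withdrawn from the study". Other ratings lead to a review. A positive Columbia suicide item or a Young Mania score above 10 "will require a psychiatric evaluation to determine if continuation in the study is appropriate". For the CGI improvement and CGI-opioid improvement scores, "Subjects will be assessed, by a study physician, for continuation in the study if they score 6 or 7". Separately, the procedure list under Subject Screening says that those with a motor threshold of 85% of stimulator output "at the initial determination of motor threshold will be removed from the study".

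**Assessments.** Under Neuropsychological scales and tests, the Brief Pain Inventory, PEG and PROMIS pain items are given at baseline and before rTMS sessions, daily or weekly. The procedure list places the pain scales in the weeks of rTMS. Under Medication use, opioid use is asked about at each session. Post-treatment Follow-up sets visits 2 and 4 weeks after rTMS is completed.

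**Analysis.** Under Statistical Analysis, a responder has at least a 50% reduction in average VAS pain score and no more than a 25% increase in morphine-equivalent dose. The section adds: "The effect of rTMS on chronic pain will be performed with a repeated measure ANOVA". It covers covariates, transformations and multiplicity. It names no analysis set and no handling of missing data.

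**The concern.** The removal wording takes a participant out of the study, not only off stimulation. Because the assessments follow the sessions, stopping sessions also stops the data that the primary outcome needs. Several triggers (mood, global and opioid ratings) are plausibly related to pain or opioid use, so the missing outcomes cannot be presumed ignorable. With no denominator or missing-response rule, the same data support several responder differences, and the plan excludes none of them. Data that were never collected cannot be recovered by a later analysis.

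**Working it through.** There is no figure in the plan to reproduce: the documents give no sample size, response rate or dropout rate.

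**Step 1. What is collected after an early exit.**
- Pain during treatment: attached to sessions or to the weeks of rTMS.
- Opioid use during treatment: attached to sessions.
- Pain and opioid use afterwards: dated from completion of rTMS.
- Safety: mania is monitored until it resolves; the non-serious events asked about after sessions are followed until they remit; a participant with an unresolved serious adverse event who discontinues "participation in the study must be followed until any of the following occurs", and the listed endpoints concern that event.

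Data up to the last session exist. No pain or opioid-use assessment is scheduled after it.

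**Step 2. How far the denominator matters.** All inputs are assumed: 20 randomised per arm, 8 active and 4 sham responders, no leaver responds. The completer difference is 8/(20 − active leavers) − 4/(20 − sham leavers).

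| Leavers, active v sham | Completers | Difference | All randomised |
|---|---|---|---|
| 6 v 2 | 8/14 v 4/18 = 57.1% v 22.2% | 34.9 points | 8/20 v 4/20 = 20.0 points |
| 2 v 6 | 8/18 v 4/14 = 44.4% v 28.6% | 15.9 points | 20.0 points |
| 2 v 2 | 8/18 v 4/18 = 44.4% v 22.2% | 22.2 points | 20.0 points |

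Fisher's exact p is 0.301 with all randomised, 0.068 among completers at 6 v 2 and 0.471 at 2 v 6.

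**Step 3. Dropping the assumption that no leaver responds.** The extreme bounds on the all-randomised difference are:
- 6 v 2: from 8/20 − 6/20 = +10 points to 14/20 − 4/20 = +50 points.
- 2 v 6: from 8/20 − 10/20 = −10 points to 10/20 − 4/20 = +30 points.

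**Step 4. Limits of counting missing as non-response.** Suppose 8 v 4 are the true responders and two of them are unobserved.
- In the active arm only: 6/20 − 4/20 = 10 points.
- In the sham arm only: 8/20 − 2/20 = 30 points.
- Two in each arm: 6/20 − 2/20 = 20 points.

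**Step 5. Equal removal rates are not a safeguard.** Let the worst-mood 20% leave each arm, with assumed pain–mood correlations of 0.6 and 0.3. With standard normal pain and mood, mean pain among those who stay shifts by r × φ(0.842)/0.80 = r × 0.350. The spurious difference between arms is (0.6 − 0.3) × 0.350 = 0.105 SD. With the same correlation in both arms it is 0.

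**Step 6. Whether a mixed model would be enough.** A simulation used baseline plus five weekly scores, no true effect, and removal in weeks 1–4 on mood correlated with the next, unrecorded pain score. Where removal rates or correlations differed by arm, absolute bias was 0.011–0.074 SD for a mixed model and 0.008–0.060 SD for a completer change contrast. The mixed model does not remove this bias. Its gain is precision: at 20 per arm its sampling SD was 7–22% lower.

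**The case against.** The strongest reply is that this is a feasibility study with exploratory efficacy. That stands and limits the weight. The protocol nevertheless names a primary effectiveness outcome and a two-sided 0.05 threshold, and a record of exits by arm serves the tolerability aim too.

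Several stronger readings are tempting, and the documents do not support them:
- *Every rating trigger is an exit.* The Columbia, Young Mania and CGI scores trigger a review that may end participation. They do not require removal.
- *The motor-threshold removal is outcome-related loss.* It comes before rTMS begins and is listed ahead of baseline pain testing. It may precede randomisation; the documents do not say.
- *No assessment time is given anywhere.* The Aim 1 hypothesis refers to pain after five weeks of treatment. Only the endpoint definition lacks a time.
- *After an early exit, only serious events are followed.* Mania and non-serious events are followed as well. That is still safety follow-up and supplies no pain or opioid-use data.
- *A completer analysis is planned.* The plan is silent. A classical repeated-measures ANOVA uses complete rows, but the text does not say that this form will be used.

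Completion of rTMS could also be read as the last session attended, which would keep the follow-up visits for leavers. Removal from the study works against that reading.

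Finally, the 20-point figure in Step 2 is correct by construction, because leavers are assumed not to respond. That is fair, and Steps 3 and 4 show what happens otherwise.

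**Conclusion.** The point holds. As written, removal ends scheduled collection of both components of the primary outcome, for reasons plausibly related to that outcome, and the responder proportion has no stated denominator or missing-response rule. The bias could go in either direction. In the illustration, a 20-point difference becomes 35, 16 or 22 points among completers. Those figures rest entirely on assumed counts and show sensitivity to the choice of denominator; they do not predict what this trial will find. A reader might infer that the result must be biased, or that a mixed model alone would put it right. The documents do not establish the first, and Step 6 contradicts the second. The weight is moderate: the change should be made, but the gap does not invalidate a feasibility study.

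**What to change.** **1. Collection.** No change to the criteria for stopping rTMS is proposed. Amend the protocol so that stopping rTMS after randomisation does not end collection of pain scores and opioid use. With consent, continue these questionnaires to week 5 and to the 2- and 4-week follow-ups, dated from the planned end of rTMS. Reconcile with this the differing removal and withdrawal wording in Subject Screening, Criteria for Early Discontinuation, the rTMS risk section and Pregnancies. State whether randomisation follows the motor-threshold check.

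**2. Primary outcome.** Assess response at the end of week 5, with all randomised participants in the denominator as allocated. Use data observed after stopping and count those still missing as non-responders. Give a completer sensitivity analysis and tabulate exits by arm and reason. State which opioid baseline applies: the week before sessions (Medication use) or the four weeks before entry (Subject Screening). Reconcile the VAS pain score in the endpoint with the schedule, which lists a VAS only for opioid craving.

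**3. Optional, for precision.** Use a likelihood-based mixed model that keeps partial records in place of a complete-row ANOVA. It does not cure removal that depends on unrecorded pain.

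**Cost.** A protocol amendment and a few extra questionnaires, by phone if needed. The comparison becomes one of assignment regardless of stopping rTMS, and the protocol should name that choice. Counting missing as non-response can still shift the difference if missingness differs by arm, so continued collection is the main remedy.

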Participants may reduce or stop using opioids through the duration of the study. Reduced opioid use may result in reduced tolerance to opioids, which increases the risk of opioid overdose if a participant resumes opioid use at the same or greater quantity and/or frequency. Participants will be informed that reduced or discontinued opioid use will result in reduced tolerance and increased risk of overdose if opioids are resumed at the same or greater quantity and/or frequency. In addition to this counseling, participants will be offered an overdose reversal kit with intranasal naloxone (which are provided by the New York City Department of Health and Mental Hygiene and stored at our outpatient research clinic STARS and offered to any participant using illicit opioids and/or participating in an opioid treatment research study). However, since we do not anticipate reductions in their methadone dose, and participants will continue to engage in normal methadone program treatment, including drug counseling, participants will be at lower risk for overdose than patients with OUD who are not on agonist replacement therapy in the community.

3. rTMS.

The main risks of rTMS are as follows:

a. Seizure: This is the greatest concern with rTMS treatment. The incidence of rTMS-induced seizures worldwide is low and roughly comparable to the estimated incidence of spontaneous seizures with antidepressant therapy (0.1–0.6 %). In addition, rTMS-induced seizures are likely to occur during or just after the rTMS treatment session (rather than after a delay) while our subjects will be under observation. In addition, there have been no reports of epilepsy or repeated spontaneous seizures occurring due to after rTMS. Since the advent of the 1998 safety guidelines, we are aware of only 8 reports of rTMS-associated seizures, and six involved either stimulus parameters exceeding the safety guidelines, or included concomitant medication or sleep deprivation, which lower the seizure threshold.

b. Lowering the Seizure Threshold: The use of concurrent medication has been implicated as a risk factor in some of the seizures reported with rTMS. These medications include tricyclic antidepressants and neuroleptics, which are not used in this study.

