In the event of a seizure, the following procedures will be employed. An MD will be in the building and immediately available during all rTMS sessions. The staff member with the subject will make sure that the participant is on the floor (cannot fall) and will clear the area of all objects. Most seizures will end spontaneously at 1 to 2 minutes. In the event that the seizure has not ended in two minutes, the hospital emergency team will be called and Lorazepam (which is stored in the room) will be administered IM (4mg). If seizures continue or recur after a ten to twelve minute observation period, an additional intravenous dose of 4 mg may be administered until the acute care medical team arrives.

Brainsway has performed studies using the TMS H-coil device in control subjects and subjects in clinical conditions, including major depressive disorder, schizophrenia, bipolar disorder, obsessive compulsive disorder, addiction, blepharospasm, Parkinson's disease, and post-traumatic stress disorder (PTSD) (Brainsway, Ltd., unpublished data). High frequency (10-20 Hz) and high intensity (<120% of motor threshold [MT]) rTMS have been administered to 209 subjects, who were treated with for a total of 3314 sessions and 143,514 pulse trains. 98 of the 209 subjects received rTMS treatments (1296 sessions, 54,432 pulse trains) without concomitant psychotropic medications (which may lower the seizure threshold) and none experienced a seizure. The remaining 111 subjects received rTMS (2018 sessions, 89,082 pulse trains) in addition to concomitant

medications that could affect seizure threshold. Three of these subjects had a seizure. Of these three, one was taking antidepressant medications (venlafaxine, mianserine, mirtazapine), another was taking medications for schizophrenia (olanzepine, citalopram and lorazepam) and the third was taking lithium and clonazepam for bipolar disorder.

The primary safety outcome will be the absence of a serious adverse event or an unresolved non-serious adverse event. For each subject, we will inquire about potential non-serious adverse events after each sessions of rTMS. We will ask about headache, hearing changes, jaw pain, and mood symptoms. If these events are reported by the subject, we will follow these daily until they remit.

The risk of pregnancy and rTMS are unknown therefore subjects who are pregnant will not be included in the study.

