An adverse event is any untoward medical occurrence in a clinical study subject. An adverse event does not necessarily have a causal relationship with the treatment. An adverse event can therefore be any unfavorable and unintended sign (including an abnormal finding), symptom, or disease temporally associated with the use of an investigational product, whether or not related to the investigational product. (Definition per International Conference on Harmonization [ICH])

This includes any occurrence that is new in onset or aggravated in severity or frequency from the baseline condition, or abnormal results of diagnostic procedures, including laboratory test abnormalities.

• Serious Adverse Event

A serious adverse event as defined by ICH is any untoward medical occurrence that meets any of the following conditions:

- Results in death
- Is life-threatening
- Requires inpatient hospitalization
- Results in persistent or significant disability/incapacity, or
- Is a congenital anomaly/birth defect

Note: Medical and scientific judgment should be exercised in deciding whether expedited reporting is also appropriate in situations other than those listed above. For example, important medical events may not be immediately life threatening or result in death or hospitalization but may jeopardize the subject or may require intervention to prevent one of the outcomes listed in the definition above. Any adverse event is considered a serious adverse event if it is associated with clinical signs or symptoms judged by investigator to have a significant clinical impact.

• Unlisted (Unexpected) Adverse Event

An unlisted adverse event, the nature or severity of which is not consistent with the applicable product information (e.g. Investigator's Brochure for an unapproved investigational product or the package insert/summary of product characteristics for an approval product) (ICH)

2. Adverse Event Classification

• Mild:

Signs or symptoms, usually transient, requiring no special treatment and generally not interfering with usual activities.

• Moderate:

Signs or symptoms that may be ameliorated by simple therapeutic measures yet may interfere with usual activities.

• Severe:

Signs or symptoms that are intense or debilitating and that interfere with usual activities. Recovery is usually aided by therapeutic measures.

3. Relationship to Investigational Device

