For all adverse events, the relationship to study device and / or procedure will be determined by the investigator, using the following terms:

- Probably related:

Follows a reasonable temporal sequence from study device delivery / retrieval, and cannot be reasonably explained by known characteristics of the patient's clinical data or the surgical procedure applied.

- Possibly related:

Follows a reasonable temporal sequence from study device delivery / retrieval but could have been produced by the patient's clinical state or by the surgical procedures regardless of the study device.

- Probably not related:

Temporal association is such that the study device is not likely to have had any reasonable association with the observed event.

- Not related:

No relationship to study device activation is perceived.

4. Adverse Event Reporting Procedures

All adverse events will be reported from the time a signed and dated informed consent form is obtained until completion of the last study-related procedure. Events meeting the definition of serious adverse events must be reported using the Serious Adverse Event Form, including serious adverse events spontaneously reported to the investigator within 30 days after the subject has completed the study (including post study follow up).

All events that meet the definition of a serious adverse event will be reported as serious adverse events, regardless of whether they are protocol-specific assessments. All adverse events, regardless of seriousness, severity, or presumed relationship to study treatment must be recorded using medical terminology in the source document and the CRF. Whenever possible, diagnoses should be given when signs and symptoms are due to a common etiology (e.g., cough, runny nose, sneezing, sore throat, and head congestion should be reported as "Upper respiratory infection"). Investigators must record in the CRF their opinion concerning the relationship of the adverse event to study treatment. All measures required for adverse event management must be recorded in the source document and reported according to sponsor instructions. In the case of a seizure, the investigators will provide to those patients experiencing a seizure a letter documenting that the seizure was experimentally produced.

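### A brief seizure, or an rTMS-induced mania that resolves, counts as a primary safety success unless the investigator classes it as serious

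*Combined protocol and SAP*

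**What the plan says.** The outcome is defined under Risks associated with the study, 3. rTMS: "The primary safety outcome will be the absence of a serious adverse event or an unresolved non-serious adverse event". No success threshold or test is attached to it, and no time is given at which resolution is judged.

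On seizure, item 3a says: "This is the greatest concern with rTMS treatment". The seizure procedure in the same section expects a short course, "Most seizures will end spontaneously at 1 to 2 minutes", and calls for the emergency team and lorazepam only beyond two minutes. On mania, items 3e and 3f say that affected subjects are handled as follows: "they will be removed from the protocol and monitored until these symptoms resolve". For the events that staff ask about after each session (headache, jaw pain, hearing, mood) the plan is: "If these events are reported by the subject, we will follow these daily until they remit".

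Adverse Event Definitions and Classifications lists five seriousness conditions: death, threat to life, inpatient admission, lasting disability and birth defect. A note adds judgement about expedited reporting of other medically important events. It then makes any event serious if its signs or symptoms are "judged by investigator to have a significant clinical impact". Neither the list nor the note names seizure or mania.

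Adverse Event Reporting Procedures sends all events to the source document and CRF, and gives a patient who has a seizure "a letter documenting that the seizure was experimentally produced". Under Serious Adverse Event Reporting Procedures, serious events "must be reported to the PI by investigational staff within 24 hours of their knowledge of event".

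**The concern.** Specific Aim 1 is feasibility and tolerability, so this outcome will be the headline safety result. A primary safety outcome should register the harm that the protocol itself ranks first, by a rule fixed in advance. Here the course that the protocol expects of most seizures is short and self-limiting. On that course the event is resolved, and it is serious only by judgement. Two trials with identical seizures could therefore report different primary safety results.

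The reporting route is affected too, because the 24-hour report to the PI is tied to serious events. There is also an inconsistency on the page: the investigators would confirm to the patient in writing that the device trial produced the seizure, while the primary safety outcome could record that subject as a success.

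**Working it through.** **Step 1: the rule.** I read the outcome per subject: success means no serious event and no unresolved non-serious event. Failure therefore has two routes only: serious, or non-serious and unresolved.

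**Step 2: apply it, using the protocol's own definitions.**

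| Event | Serious? | Resolved? | Score |
|---|---|---|---|
| Seizure leading to admission, threat to life or lasting disability | Yes, by the list | Either | Failure |
| Seizure over two minutes, emergency team and lorazepam used | Probably, by judgement | Either | Probably failure |
| Seizure ending in 1 to 2 minutes, judged clinically significant | Yes, by judgement | Yes | Failure |
| The same seizure, not so judged | No | Yes | **Success** |
| rTMS-induced mania, subject removed, then resolves, not so judged | No | Yes | **Success** |
| Hearing change that persists | No | No | Failure |

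Rows three and four are the same clinical event with opposite scores. Only the investigator's judgement separates them.

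**Step 3: effect on the reported figure.** The documents give no sample size. I assume 20 active subjects, with 10 as an alternative, one brief seizure and no other failures. Intervals are exact (Clopper-Pearson) 95%; when all n succeed the lower limit is 0.025^(1/n).

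- n = 20, seizure classed non-serious: 20/20 = 100%, lower limit 0.025^(1/20) = 83.2%. Seizure counted: 19/20 = 95% (75.1% to 99.9%).
- n = 10, seizure classed non-serious: 10/10 = 100%, lower limit 0.025^(1/10) = 69.2%. Seizure counted: 9/10 = 90% (55.5% to 99.7%).

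**Step 4: the same rule on the protocol's H-coil series.** Three of 111 subjects on concomitant medication had a seizure, and the seriousness of those seizures is not stated. As far as seizures go, the rule could return anything from (111 − 3)/111 = 97.3% to 111/111 = 100%.

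**Step 5: workload if every seizure were reported as serious.** Expected seizures in 20 active subjects are 20 × p.

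- Per subject: 20 × 3/209 = 0.29; 20 × 3/111 = 0.54.
- Scaled to 25 sessions (five weeks of five days): 1 − (1 − 3/3314)^25 = 2.24%, giving 0.45; 1 − (1 − 3/2018)^25 = 3.65%, giving 0.73.
- Upper 95% limits: 20 × 7.70% (for 3/111) = 1.5. Per session, the Poisson limit of 8.77 events over 2018 sessions is 0.434%, or 10.3% over 25 sessions, giving 2.1.
- Item 3a's 0.1–0.6% is printed for antidepressant therapy and called only roughly comparable. If borrowed, it gives 0.02 to 0.12.

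**The case against.** The strongest reply is that the bad case needs an unlikely classification. Investigators who call seizure their greatest concern, and who write a letter about it, would have to decide that it lacked significant clinical impact. The note on medically important events points the same way, and it also invites judgement on expedited reporting beyond the five conditions. Removal for mania would likewise be hard to call insignificant, and it would be visible as a discontinuation. All this stands as a statement of likelihood. It does not make the classification a rule: neither sentence names seizure or mania or sets a criterion.

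The second reply is that little is lost. Every event reaches the CRF whatever its seriousness, a physician is immediately available at each session, and no decision hangs on the outcome. This also stands. The loss is in how the primary outcome is scored and in the guaranteed 24-hour route; the event is still captured.

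A reader might also infer that the unresolved limb does almost no work, because events are followed until they remit. The documents do not support that. Follow-up is monitoring and does not guarantee remission. Daily follow-up is stated only for the solicited events, and a lasting hearing change or jaw pain would fail the limb.

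**Conclusion.** The point holds in limited form. The stated rule can score a brief seizure, or a mania that ended treatment, as a primary safety success, and only a discretionary call prevents it. With one such event the reported success rate differs by 5 percentage points at an assumed 20 active subjects and by 10 points at an assumed 10. The finding itself rests on the wording and not on those sample sizes.

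Two stronger readings should be resisted.

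- A reader might turn the H-coil series into a probability that the outcome will be misscored. The chance of at least one seizure in 20 subjects, 1 − (1 − p)^20, is 25% at 3/209 and 42% at 3/111, and 52% at 3/2018 scaled to 25 sessions. That is the chance of a seizure. Misscoring also needs a non-serious classification, for which the documents give no rate. The series may overstate the risk here: there were 0 seizures in 98 unmedicated subjects (upper limit 3.7%), seizure disorder is an exclusion criterion, and exclusion 7 bars neuroleptics and other medications known to raise seizure risk. At 0.1–0.6% the chance is 2% to 11%. None of these figures supports the severity of the point.
- A reader might infer that the plan would re-treat a subject after a seizure, because Criteria for Early Discontinuation does not mention one. No text directs re-treatment, so that is missing detail and forms no part of this point.

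The change should be made, because it is cheap and removes discretion from the risk that the protocol ranks first.

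**What to change.** Make two changes by amendment.

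1. Under Risks associated with the study, 3. rTMS, define the outcome as: *the absence of any serious adverse event, any seizure or rTMS-induced mania (whatever its seriousness or resolution), and any non-serious adverse event unresolved at the 4-week visit.* That visit already exists, and naming it also fixes when resolution is judged.
2. Under Adverse Event Definitions and Classifications, Serious Adverse Event, add: *Any seizure is reported as a serious adverse event, whatever its duration.* This brings every seizure into the 24-hour report to the PI.

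No visits or assessments are added. The cost is at most a few extra serious adverse event forms: 0.3 to 0.7 expected in 20 assumed active subjects at the series' point rates, and 1.5 to 2.1 at the upper limits. Any sham-arm seizure would add to this, and the documents give no rate for it. The other cost is a possibly less favourable safety figure.
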